### 2.2. Study Design

- This is a randomized, open-label study in which subjects will receive either 13vPnC with 2-PE from an MDV or 13vPnC without 2-PE in a PFS (see [Table 2](#)).
- Subjects will be randomized in a 1:1 ratio to 1 of the 2 groups.
- Subjects will be vaccinated in a 3-dose infant series followed by a toddler dose.
- Subjects will have 2 blood draws of up to 5 mL at approximately 1 month after the infant series and approximately 1 month after the toddler dose.

**Table 2. Study Vaccination Schedule**

Randomization Group	Visit 1 6 Weeks	Visit 2 10 Weeks	Visit 3 14 Weeks	Visit 5 12 Months
Group 1: MDV	MDV DTP-Hib-HBV Rotavirus vaccine	MDV DTP-Hib-HBV Rotavirus vaccine	MDV DTP-Hib-HBV Rotavirus vaccine	MDV Hepatitis A virus vaccine
Group 2: PFS	PFS DTP-Hib-HBV Rotavirus vaccine	PFS DTP-Hib-HBV Rotavirus vaccine	PFS DTP-Hib-HBV Rotavirus vaccine	PFS Hepatitis A virus vaccine

Abbreviations: DTP-Hib-HBV = diphtheria, tetanus, and pertussis; *Haemophilus influenzae* type b; and hepatitis B virus vaccine; MDV = multidose vial; PFS = prefilled syringe.

### 3. ENDPOINTS AND BASELINE VARIABLES: DEFINITIONS AND CONVENTIONS

#### 3.1. Primary Endpoints

- Incidence of local reactions and systemic events at the following time periods in the MDV group and in the PFS group:
  - Within the 7 days after the first dose of the infant series.
  - Within the 7 days after the second dose of the infant series.
  - Within the 7 days after the third dose of the infant series.
  - Within the 7 days after the toddler dose.
- Incidence of adverse events (AEs) in the MDV group and in the PFS group from the first dose up to 1 month after the infant series.
- Incidence of AEs in the MDV group and in the PFS group from the toddler dose up to 1 month after the toddler dose.
- Incidence of serious adverse events (SAEs) in the MDV group and in the PFS group from the first dose up to 1 month after the toddler dose.
- Incidence of newly diagnosed chronic medical conditions in the MDV group and in the PFS group from 1 month after the infant series up to the toddler dose.

Each day of vaccination will be considered Day 1.

#### 3.2. Secondary Endpoints

- The proportion of subjects with immunoglobulin G (IgG) concentrations equal to or above the defined threshold for each of the pneumococcal serotypes measured:
  - 1 month after the infant series in the MDV group and in the PFS group.
  - 1 month after the toddler dose in the MDV group and in the PFS group.

- The serotype-specific IgG geometric mean concentration (GMC) for each of the pneumococcal serotypes measured:
  - 1 month after the infant series in the MDV group and in the PFS group.
  - 1 month after the toddler dose in the MDV group and in the PFS group.
- The serotype-specific opsonophagocytic activity (OPA) geometric mean titer (GMT) for each of the pneumococcal serotypes measured:
  - 1 month after the infant series in the MDV group and in the PFS group.
  - 1 month after the toddler dose in the MDV group and in the PFS group.
- The proportion of subjects achieving a serotype-specific OPA titer  $\geq$  the lower limit of quantitation (LLOQ) for each of the pneumococcal serotypes measured:
  - 1 month after the infant series in the MDV group and in the PFS group.
  - 1 month after the toddler dose in the MDV group and in the PFS group.

The defined thresholds for IgG are listed below:

- $\geq 0.35$   $\mu\text{g/mL}$  will be used for serotypes 1, 3, 4, 5, 6A, 7F, 9V, 14, 18C, 19F, and 23F.
- $\geq 0.23$   $\mu\text{g/mL}$  will be used for serotype 5.
- $\geq 0.10$   $\mu\text{g/mL}$  will be used for serotype 6B.
- $\geq 0.12$   $\mu\text{g/mL}$  will be used for serotype 19A.

### 3.3. Other Endpoints

Not applicable.

### 3.4. Baseline Variables and Study Conduct

#### 3.4.1. Demographic, Medical History, and Baseline Characteristic Variables

The demographic variables are age at randomization/first vaccination visit (in days), sex, race, ethnicity, and baseline weight. Age, in days, will be calculated as (randomization/first vaccination date – date of birth + 1). Weight at the time of the first vaccination (enrollment) is the baseline weight measured on the day of the first vaccination. Ages at the other vaccinations will also be compiled.

Medical history will be categorized according to the Medical Dictionary for Regulatory Activities (MedDRA).

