3.3. Approximate Number of Subjects

Approximately 300 subjects (150 subjects per group) will be randomized in this study at approximately 8 sites. The number of subjects enrolled at each site may vary based on enrollment capabilities of each site and the final number of sites.

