4.1. Inclusion Criteria

Subjects must meet all of the following inclusion criteria to be eligible for enrollment into the study:

1. Evidence of a personally signed and dated informed consent document indicating that the parent(s)/legal guardian(s) has/have been informed of all pertinent aspects of the study.
2. Parent(s)/legal guardian(s)/caregiver(s) willing and able to comply with scheduled visits, treatment plan, and other study procedures.
3. Aged 6 weeks (42 to 72 days) at the time of vaccination. (The day of birth is considered Day 0.)
4. Available for the entire study period and whose parent(s)/legal guardian(s)/caregiver(s) can be reached by telephone.
5. Healthy infant as determined by medical history, physical examination, and judgment of the investigator.
6. Weight of 3.0 kg or greater at the time of vaccination.

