6.1.1. Infant Series (6, 10, and 14 Weeks of Age)

6.1.1.1. Visit 1 (42 to 72 Days of Age)

- Obtain informed consent per local requirements from the subject's parent(s)/legal guardian(s) before performing study-specific procedures.
- Record the subject's demographic information (including date of birth, sex, and ethnicity).
- Obtain and record the subject's medical history including prior vaccinations.
- Perform a physical examination evaluating any clinically significant abnormalities within the following body systems: general appearance; skin; head, eyes, ears, nose, and throat; heart; lungs; abdomen; extremities; neurological; musculoskeletal; and lymph nodes; including worsening of medical history conditions.
- Weigh the subject.
- Ensure that all inclusion criteria, none of the exclusion criteria, and none of the temporary delay criteria are met.

- On the day of vaccination, prior to vaccination, measure and record the subject's axillary temperature.
- After all entry criteria are confirmed, the subject will be randomized into 1 of the 2 vaccine groups using an IRT system (IWR), or equivalent system. An appropriate site staff member will use the IRT system to obtain the subject's investigational product DU or container number.
- Administer a single 0.5-mL intramuscular injection of 13vPnC from either an MDV or a PFS into the anterolateral thigh muscle of the left leg.
- Administer a single intramuscular dose of DTP-Hib-HBV into a different limb from that used to administer 13vPnC, according to local clinical practice.
- Administer a single dose of rotavirus vaccine according to local clinical practice.
- Observe the subject for at least 30 minutes after vaccination for any significant acute reactions. Any AEs noted during the observation period should be recorded in the subject's source documents and on the AE section of the CRF.
- Issue a caliper and a digital thermometer to the parent(s)/legal guardian(s)/caregiver(s) and provide instructions on their use.
- Issue a subject electronic diary (e-diary) to the parent(s)/legal guardian(s)/caregiver(s). Provide instruction on its completion for 7 days (Day 1 through Day 7, where Day 1 is the day of vaccination).
- Ask the parent(s)/legal guardian(s)/caregiver(s) to contact the investigator immediately if any significant illness or hospitalization occurs during the study period, or if the subject experiences a large (>14 caliper units) local reaction.

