### 4.1. Evaluable Analysis Populations

The evaluable immunogenicity population will be defined for the 3-dose infant series and the toddler dose separately.

The infant evaluable immunogenicity population will include all subjects who:

1. met all eligibility criteria,
2. were aged 6 weeks (42 to 72 days, inclusive) at the time of the first vaccination,
3. have received 3 doses of vaccine that was randomly assigned to them,

4. have post–Dose 3 blood drawn within 27 to 56 days, inclusive, after the third vaccination,
5. have at least 1 valid and determinate post–Dose 3 assay result, and
6. have no other major protocol violations.

The toddler evaluable immunogenicity population will include all subjects who:

1. met all eligibility criteria,
2. have received 3 doses in the infant series and 1 toddler dose of randomly assigned vaccine,
3. have post–Dose 4 blood drawn within 27 to 56 days, inclusive, after the fourth vaccination,
4. have at least 1 valid and determinate post–Dose 4 assay result, and
5. have no other major protocol violations.

The infant and toddler evaluable immunogenicity populations will be the primary immunogenicity populations for the infant and toddler analyses.

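### The SAP's age formula adds one day to the protocol's Day 0 count, and if it is used for the 42 to 72 day check it excludes eligible infants vaccinated on day 72 from the infant evaluable population

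*SAP*

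**What the plan says.** Protocol 4.1, inclusion criterion 3, sets both the age window and the way days are counted: "Aged 6 weeks (42 to 72 days) at the time of vaccination. (The day of birth is considered Day 0". The heading of the first visit gives the same window: "6.1.1.1. Visit 1 (42 to 72 Days of Age".

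SAP 3.4.1 names the variable, "The demographic variables are age at randomization/first vaccination visit (in days), sex, race, ethnicity, and baseline weight", and then gives its formula: "Age, in days, will be calculated as (randomization/first vaccination date – date of birth + 1". The same section says that ages at the other vaccinations will be compiled, without a separate formula for them.

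SAP 4.1 builds the infant evaluable immunogenicity population from a numbered list. Criterion 1 is "met all eligibility criteria". Criterion 2 is "were aged 6 weeks (42 to 72 days, inclusive) at the time of the first vaccination". The section also fixes the role of this population: "The infant and toddler evaluable immunogenicity populations will be the primary immunogenicity populations for the infant and toddler analyses".

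**The concern.** The two documents count age differently. With birth as Day 0, age is the vaccination date minus the date of birth. Adding 1 makes the day of birth Day 1. The SAP does not acknowledge the change, and its window in 4.1 has not been moved to 43 to 73 to absorb it.

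Two things follow. Reported ages at first vaccination sit one day above the protocol's count for every child. And because SAP 4.1 checks age again, separately from eligibility, the extra day can act at the edge of an analysis population: a correctly enrolled infant could be dropped from the primary population for the infant immunogenicity analyses by the derivation alone.

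**Working it through.** **Inputs.**
- Window: 42 to 72 days inclusive (Protocol 4.1; SAP 4.1, criterion 2).
- Protocol count: day of birth is Day 0 (Protocol 4.1).
- SAP count: date difference plus 1 (SAP 3.4.1).
- Number randomized: about 300, or 150 per group (Protocol 3.3).

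**Formulas.** Let d be the first vaccination date minus the date of birth.
- Protocol age = d
- SAP age = d + 1

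**The protocol's own figure.** Six weeks is 6 × 7 = 42 days, which matches the protocol's lower bound under the Day 0 count. The SAP formula gives 42 + 1 = 43 for the same infant.

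**Both counts against the 42 to 72 window.**

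| d | Protocol age | In window? | SAP age | In window? |
|---|---|---|---|---|
| 41 | 41 | no | 42 | yes |
| 42 | 42 | yes | 43 | yes |
| 71 | 71 | yes | 72 | yes |
| 72 | 72 | yes | 73 | **no** |
| 73 | 73 | no | 74 | no |

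The window holds 72 − 42 + 1 = 31 eligible ages. Only one of them, day 72, fails under the SAP formula. At the other end, an infant at d = 41 would pass criterion 2 under the SAP formula. That infant does not meet inclusion criterion 3, so criterion 1 still removes the infant from the population.

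**Number affected.** The documents give no distribution of age at enrolment, so the share vaccinated on exactly day 72 has to be assumed. Number affected = 300 × share:

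| Assumed share on day 72 | Of 300 | Per group of 150 |
|---|---|---|
| 0.5% | 1.5 | 0.75 |
| 1% | 3.0 | 1.5 |
| 3.2% (1/31, uniform) | 9.7 | 4.8 |
| 5% | 15 | 7.5 |

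The base is all randomized infants. Some of these would be non-evaluable for other reasons, so the number lost through this criterion alone would be somewhat lower.

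**Without the plus one.** Day 72 gives 72 and passes, all 31 eligible ages pass, and day 41 gives 41 and fails, as in the protocol.

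**Later ages.** If the same formula were carried to the toddler dose, the Visit 5 window of 365 to 420 days would be reported as 366 to 421. No population criterion depends on those ages.

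**The case against.** The strongest reply is that the exclusion is inferred. The formula sits in a section on demographic and baseline variables, and SAP 4.1 does not refer back to it. Criterion 2 closely follows the wording of inclusion criterion 3, where the Day 0 rule is stated, and can be read as the same check on the same count. This stands as a limit: a reader might infer that day-72 infants are certain to be dropped, and the SAP does not say so. It does not remove the problem. The SAP gives only one formula for age in days, for the same time point, and nothing tells a programmer to use another. If criterion 2 were programmed on Day 0, the SAP would carry two ages for one visit. The demographic summaries by population (SAP 6.3.2) could then show an infant aged 73 days in a population capped at 72.

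A reader might also infer that underage infants enter the evaluable population. They do not, because criterion 1 removes them. Nor should a loss of about 10 of 300 be taken as expected: it needs enrolment spread evenly over the 31 days, whereas the visit is labelled and described as a 6-week visit, at the lower edge of the window.

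The remaining points limit the consequence, and they stand:
- The primary objective is safety, and the safety populations (SAP 4.3) have no age criterion.
- All immunogenicity endpoints are also analysed in the all-available populations (SAP 4.2 and 6.2), which would keep these infants.
- The toddler evaluable population has no separate age criterion.
- The analysis is descriptive, with no hypothesis tests (SAP 5.1).
- Age at first vaccination should be unrelated to the randomized group, so a loss of this kind should not favour either arm.
- Reasons for exclusion from the evaluable population are summarized (SAP 6.3.1), so a wrong age exclusion could be noticed.

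**Conclusion.** The contradiction is in the current text of both documents. The one-day overstatement of age at first vaccination follows from the formula, with no assumption about age distribution or programming. It is the same in both groups and changes no comparison between them.

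The wrongful exclusion of infants vaccinated on protocol day 72 from the infant evaluable population follows only if criterion 2 is programmed with the SAP 3.4.1 formula. That is the natural reading, but it is not stated. Under that condition the size depends on the unknown share of infants vaccinated on exactly day 72: about 1.5 to 15 of 300 for shares of 0.5% to 5%, and probably towards the low end. The effect is confined to the primary population for the infant immunogenicity analyses, a secondary objective. It is a small defect, but a stated rule that gives a wrong result at a population boundary should be corrected.

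**What to change.** In SAP 3.4.1, remove the plus one, so that age in days is the vaccination date minus the date of birth. State that the day of birth is Day 0 for all ages in the SAP, including ages at later vaccinations and the 42 to 72 day check in SAP 4.1.

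A lesser alternative is to state only that criterion 2 in SAP 4.1 uses the protocol's Day 0 count. That settles the population but leaves reported ages one day off the protocol's count, with two conventions in one document.

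The cost is one line of SAP wording and one line of derivation code. No eligibility rule, visit window or study procedure changes.

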### 3.4.2. E-Diary Completion

An electronic diary (e-diary) will be considered transmitted if any data for the local reactions or the systemic events are present on any day. If all data are missing for all items on the e-diary for every day following vaccination, then the e-diary will be considered not transmitted.

For transmitted e-diaries, the following variables will be defined: “Day 1,” “Day 2,” “Day 3,” “Day 4,” “Day 5,” “Day 6,” “Day 7,” and “Day 1 to Day 7.”

An e-diary will be considered complete if all expected data for all 7 days are available (ie, not missing) and data are valid. Otherwise, the e-diary will be considered incomplete.

For any given day, an e-diary will be considered complete if all expected data are available.

For completed e-diaries, the following variables will be defined: “Day 1,” “Day 2,” “Day 3,” “Day 4,” “Day 5,” “Day 6,” “Day 7,” and “Day 1 to Day 7.”

For e-diaries that are incomplete, an indicator variable for the percentage of days without data will be derived as follows:

- =1, if data have been transmitted and are complete for 7 days (100%).
- =2, if data have been transmitted and are complete for 6 days ( $\geq 75\%$  to  $< 100\%$ ).
- =3, if data have been transmitted and are complete for 4 or 5 days ( $\geq 50\%$  to  $< 75\%$ ).
- =4, if data have been transmitted and are complete for 2 or 3 days ( $\geq 25\%$  to  $< 50\%$ ).
- =5, if data have been transmitted and are complete for 0 or 1 day ( $< 25\%$ ).

### 3.4.3. Concomitant Vaccine(s)

Nonstudy vaccines will be categorized according to the World Health Organization (WHO) Drug Dictionary (WHODD).

## 3.5. Safety Endpoints

### 3.5.1. Adverse Events

A 3-tier approach will be used to summarize AEs. Under this approach, AEs are classified into 1 of 3 tiers. Different analyses will be performed for different tiers (see [Section 6.4.1](#)).

Tier 1 events: These are prespecified events of clinical importance and are maintained in a list in the product’s safety review plan.

Tier 2 events: These are events that are not tier 1 but are “common.” A MedDRA preferred term is defined as a tier 2 event if there are at least 4 subjects with the given preferred term in any vaccine group.

Tier 3 events: These are events that are neither tier 1 nor tier 2 events.

### 3.5.2. Reactogenicity Endpoints

Reactogenicity data captured in the e-diary consist of local reactions (redness, swelling, and pain at the injection site [tenderness]) and systemic events (fever, decreased appetite [loss of appetite], drowsiness [increased sleep], and irritability [fussiness]).

#### 3.5.2.1. Local Reactions

Local reactions reported in the e-diary are redness, swelling, and pain at the injection site (tenderness).

Redness and swelling will be measured and recorded in caliper units (range: 1 to 14 and >14) for the first 7 days following vaccination (Days 1 to 7), and then categorized using the scale shown in Table 3 below. The measurements will then be recorded in the e-diary.

A caliper will be given to the subject's parent(s)/legal guardian(s)/caregiver(s) with instructions for measuring both redness and swelling at the injection site. Each caliper unit is equivalent to 0.5 cm. The parent(s)/legal guardian(s)/caregiver(s) will be asked to measure the largest diameters of the local reaction. When a caliper measurement is between 2 values, the higher value should be reported. At the time of entry into the e-diary, the parent(s)/legal guardian(s)/caregiver(s) should record the maximum severity of the reaction since the previous entry into the e-diary.

**Table 3. Local Reaction Grading Scale**

	GRADE 1 Mild	GRADE 2 Moderate	GRADE 3a Severe
Redness	1 to 4 caliper units (or measuring device units) = 0.5 to 2.0 cm	5 to 14 caliper units (or measuring device units) = 2.5 to 7.0 cm	>14 caliper units (or measuring device units) = >7.0 cm
Swelling	1 to 4 caliper units (or measuring device units) = 0.5 to 2.0 cm	5 to 14 caliper units (or measuring device units) = 2.5 to 7.0 cm	>14 caliper units (or measuring device units) = >7.0 cm
Pain at injection site (tenderness)	Hurts if gently touched (eg, whimpers, winces, protests, or withdraws)	Hurts if gently touched (with crying)	Causes limitation of limb movement

a. Local reactions >14 caliper units (>7.0 cm) should be assessed by the study site.

Although the e-diary was designed in such a way that the parent could not skip a question without answering it, the possibility of conflicting responses still exists. For redness and swelling, caliper units could be recorded as no or the root question could be missing an answer; or redness/swelling could be recorded as yes with a caliper unit of zero (if defaulted by the database). The combination of no with a caliper unit recorded will result in the answer to the root question being considered yes. The combination of yes with a caliper unit equal to 0 will result in the caliper unit being considered “>0.” A missing value for the root question with a positive value for caliper units will result in the answer to the root question being considered yes. These rules are summarized in Table 4 below.

**Table 4. Data Conventions for Redness and Swelling in the Presence of Inconsistent or Missing Responses**

Reported Response		Recoded Response	
Present	Caliper Units	Present	Caliper Units
Missing	Missing	Missing	Missing
Missing	0	Missing	Missing
Missing	1-14	Yes	1-14
Missing	>14	Yes	>14
Yes	Missing	Yes	Missing
Yes	0	Yes	>0
Yes	1-14	Yes	1-14
Yes	>14	Yes	>14
No	Missing	No	Missing
No	0	No	Missing
No	1-14	Yes	1-14
No	>14	Yes	>14

Redness and swelling will be further categorized according to the following scale based on the recoded responses:

= missing, if both variables (presence/absence and caliper units) are missing or otherwise unavailable, or if present (ie, yes) and caliper units are missing.

=0 (absent), if not present (ie, no) and caliper units are missing.

=1 (mild), if present and the area is 0.5 to 2.0 cm (1 to 4 caliper units), or if present and caliper units are >0.

=2 (moderate), if present and the area is 2.5 to 7.0 cm (5 to 14 caliper units).

=3 (severe), if present and the area is >7.0 cm (>14 caliper units).

In addition, the maximum diameter of the affected area for redness and swelling will be determined. The maximum diameter will be derived as follows:

= xx (maximum actual value), if present on at least 1 day in the required interval and caliper units are >0.

= missing, if values are a mixture of absent and missing for the required days in the interval.

=0, if all values are absent for all required days in the interval.

For the purpose of creating an indicator variable for tenderness on each day, the following algorithm will be used:

=1 (present), if tenderness is recorded as present or as interferes with limb movement.

=0 (absent), if tenderness is recorded as none discernible.

= missing, if tenderness is missing.

For the local reactions, 3 more derivations are required: whether or not a specific reaction occurred on “any day,” whether or not the subject experienced “any local reaction” on a given day, and whether or not the subject experienced “any local reaction” on “any day.”

For the occurrence of a specific reaction on “any day,” the following algorithm is used and is summarized in Table 5:

=1 (yes), if the subject reports the specified reaction as yes (or present) on any day in the required interval.

=0 (no), if the subject reports the specified reaction as no (or absent) for all days in the required interval.

= missing, if the subject reports the specified reaction as a combination of no and missing for all days in the required interval.

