7.1. Safety Assessments

Safety parameters will be assessed as described in the schedule of activities, and below.

A medical history and physical examination including measurement of vital signs will be performed on all subjects at Visit 1. Significant medical history and observations from the physical examination will be documented in the CRF.

The safety parameters include e-diary reports of local reactions at the 13vPnC injection site and systemic events that occur in the 7 days after investigational product administration. These prospectively collected occurrences of local reactions and systemic events are graded as described in Section 7.1.

Acute reactions within the first 30 minutes after investigational product administration will be assessed and documented in the AE CRF.

In addition, AEs and SAEs are collected, recorded, and reported as defined in [Section 8](#).

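### The SAP derives tenderness only as present, absent or missing, with labels that do not match the pain grades in Table 3, so no prespecified output isolates Grade 3 pain

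*SAP*

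**What the plan says.** **Collection.** Table 3 is the same in protocol 7.1.2 and SAP 3.5.2.1. It grades pain as mild (a reaction to light touch), moderate (the same with crying) and severe: "Causes limitation of limb movement". Parents are to record the worst severity since the previous diary entry. Protocol 7.1 adds: "These prospectively collected occurrences of local reactions and systemic events are graded as described in Section 7.1".

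**Derivation for pain.** SAP 3.5.2.1 introduces its rule with "For the purpose of creating an indicator variable for tenderness on each day, the following algorithm will be used". The codes are "1 (present), if tenderness is recorded as present or as interferes with limb movement", "0 (absent), if tenderness is recorded as none discernible", and missing if tenderness is missing. No other tenderness variable is defined.

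**Derivation for redness and swelling.** SAP Table 4 recodes conflicting answers, and a 0-to-3 grade follows. "The combination of yes with a caliper unit equal to 0 will result in the caliper unit being considered" greater than zero. The mild grade then covers 1 to 4 units, "or if present and caliper units are >0". A reaction marked as present with missing units is given a missing grade.

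**Reporting.** The endpoint in SAP 3.1 is incidence. SAP 6.1 promises a number, a proportion and a 95% CI per group and dose, with no breakdown by grade. SAP 6.4.2 lists subjects who had an unscheduled visit for a Grade 3 reaction.

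**The concern.** Pain is the exception among the graded diary items. Redness, swelling, appetite, drowsiness and irritability each have a 0-to-3 code, and fever has 0 to 4. Pain has a three-level scale at collection and a two-level variable at analysis.

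The labels in the rule are also not those of Table 3, so a programmer must guess where moderate pain goes. The primary objective is to describe the safety profile with and without 2-PE. If the SAP is followed as written, the report could say how many infants had any tenderness after each dose, but not how many had severe tenderness.

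For redness and swelling, two ways of recording a reaction of unknown size receive different grades, and the SAP gives no reason.

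**Working it through.** The point rests on derivation rules, so the main check sets the rules side by side.

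**1. Pain: Table 3 against the tenderness code**

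| Table 3 grade | Matching label in the SAP rule | Code |
|---|---|---|
| none | none discernible | 0 |
| 1, light touch | none exact; presumably present | 1 |
| 2, with crying | none exact; presumably present | 1 |
| 3, limb movement limited | interferes with limb movement | 1 |

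Three grades map to one code, so Grade 3 cannot be recovered from the derived variable. Incidence is preserved only if present is read as covering Grades 1 and 2. Taken literally, a record of pain with crying matches none of the listed conditions.

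**2. Could another planned output show severe pain?**

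- SAP 6.1: no breakdown by grade.
- SAP 6.4.2: requires an unscheduled visit. Protocol 6.1.5 requires that visit when a reaction exceeds 14 caliper units. Pain is assessed at the visit, but pain alone is not a stated trigger. The contact instruction at each vaccination visit likewise names size, not pain.
- AE tables: under protocol 7.1.1, diary events need not be entered as AEs.

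None provides a count of Grade 3 pain.

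**3. Redness and swelling: the 12 rows of SAP Table 4 passed through the grading rules**

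| Rows | Result |
|---|---|
| 3 (units >14; root question missing, Yes or No) | severe |
| 3 (units 1-14; root question missing, Yes or No) | mild for 1-4, moderate for 5-14 |
| 3 (Missing/Missing, Missing/0, Yes/Missing) | missing |
| 2 (No/Missing, No/0) | absent |
| 1 (Yes/0) | mild, with no measured size |

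Check: 3 + 3 + 3 + 2 + 1 = 12. Two rows mean present with size unknown (Yes/0 and Yes/Missing), and only the first is graded mild. Both stay Yes after recoding, so both count towards incidence.

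Read literally, the added mild clause is also true of a measured 9 units (moderate) and of any value above 14 (severe). It is evidently meant for the recoded value alone. The maximum-diameter rule has a related gap: it asks for the actual value when units exceed zero, and a recoded Yes/0 has none.

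**4. Scale.** Protocol Table 5 uses 1 − (1 − p)^150. It reproduces: p = 0.6% gives 59.5%, and p = 0.2% gives 25.9%. The documents give no rate of Grade 3 pain, so the rates below are assumptions per dose in a group of 150.

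| Assumed rate | Expected children (150 × p) | Chance of at least one |
|---|---|---|
| 0.5% | 0.75 | 52.9% |
| 1% | 1.5 | 77.9% |
| 2% | 3.0 | 95.2% |
| 5% | 7.5 | 99.95% |

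As a hypothetical case, let half of each group have some pain, with Grade 3 pain in 5% of one group and 1% of the other. The SAP variable shows 50% against 50%, and the 4-point difference in severe pain is not visible.

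**The case against.** The strongest reply is that the rule does what it says. It is labelled an indicator, it feeds the any-day and any-reaction derivations, and those need only yes or no. The primary endpoint is incidence, there are no hypotheses or decision rules, and an indicator does not erase a recorded grade. Protocol 7.1 says that reactions are graded; it does not promise a comparison of severity between groups. All of this stands. It limits the point to the description of severity, but it does not supply the missing pain-severity variable or summary.

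A reader might go further and infer that the SAP hides or under-grades severe reactions in general, or that redness and swelling of unknown size are always called mild. The documents do not support either. Units above 14 are intended to be graded severe in all three Table 4 rows where they occur, even when the root question is No or missing. Only Yes/0 becomes mild; Yes/Missing does not. The SAP attributes the zero to a possible database default, says that diary questions could not be skipped, and gives no frequency. A very large reaction also has a second route, through parent contact, a site visit with measured diameters, and the SAP 6.4.2 listing. That route does not cover severe pain alone, or a Yes/0 entry whose true size was 5 to 14 units.

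Nor can pain be said to be treated worse than the other local reactions in the tables: the SAP states no by-grade tabulation for any of them.

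**Conclusion.** The concern holds as a gap in derivation and reporting. No prespecified variable, summary or listing separates Grade 3 pain, and the tenderness labels do not match the scale in either document. The primary incidence result does not change, on the assumption that present covers Grades 1 and 2. What is missing is the severity description of one of three local reactions, after each of four doses. Its numerical effect cannot be derived from the documents; the rates above are assumptions.

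The redness and swelling point is secondary. It concerns one of 12 recoding rows plus a loosely worded clause. It can affect grade only, not incidence, and may be rare.

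One uncertainty remains. The documents do not show the diary's response options for pain. If the diary offers the Table 3 grades, the SAP labels are simply wrong. If it offers the SAP's three labels, Grade 3 could still be separated, but Grades 1 and 2 could not, and the collection would differ from protocol Table 3.

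**What to change.** In SAP 3.5.2.1:

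- Derive tenderness daily as 0, 1, 2, 3 or missing in Table 3 wording, and state how each actual diary response maps to a grade. Define any tenderness as Grade 1 or more.
- Limit mild redness and swelling to 1 to 4 units.
- Treat Yes/0 and Yes/Missing alike, as present with severity unknown in a row of their own. Alternatively, keep mild for Yes/0 and report how many entries were graded that way. In either case, say how Yes/0 enters the maximum diameter.

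In SAP 6.1, state a maximum-grade summary by dose and vaccine group for redness, swelling and pain.

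The cost is SAP text, derivation programming and table shells. If the diary records the Table 3 grades, no new data and no change to the endpoint are needed. The diary specification should be checked first.
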